11.5.1.1.1 Estimand for the Primary Efficacy Analysis	The second will be a sensitivity analysis using a pattern-mixture model. The commonly applied “copy reference” method may be employed.	The second will be a sensitivity analysis using a pattern-mixture model.	Correction
11.5.1.2 Secondary Efficacy Parameters		
COVID-19 impact assessment score at each visit.	Additional secondary endpoint for assessment of COVID-19 impact
11.5.1.2.4 COVID-19 Impact Assessment Score at each Visit		11.5.1.2.4 COVID-19 Impact Assessment Score at each Visit The COVID-19 impact assessment score will be summarized at each visit.	Addition to align with additional secondary endpoint
11.6 Safety Analysis		Safety data collected outside of planned visit windows but within allowance limits (up to 1 week late for Visits 7 and 8) will be included in the summary tables. Safety data collected outside of planned visit windows and outside of the allowance limits (>1 week to 6 weeks late for Visits 7 and 8) will be listed, but will not be included in the summary tables. Subgroup analyses may be performed to assess the impact of COVID-19 on the safety analyses.	Addition to align with changes in Section 8.2.2.1
11.6.1.1 Adverse Events		Each AE summary described above will be presented as all AEs, AEs that are associated with the COVID-19 pandemic (as determined by	Addition to consider COVID-19 impact in summary of safety data

CONFIDENTIAL

Location in Amended Protocol	Original Text (Final Protocol Version 2.0 dated 15 Mar 2019)	Revised Text in Amended Protocol (Protocol Version 3.0 dated 30 June 2020)	Rationale for Change
		the investigator), and AEs that are not associated with the COVID-19 pandemic. AEs associated with the COVID-19 pandemic will be listed separately.	
11.8 Interim Analyses	If the estimated pooled standard deviation is larger than the assumed pooled standard deviation in the sample size calculation (see Section 11.9), sample sizes in placebo and escitalopram treatment groups may be increased to ensure an adequate power.	If the estimated pooled standard deviation is larger than the assumed pooled standard deviation in the sample size calculation due to assumption deviation as well as COVID-19 remote visits (see Section 11.9), sample sizes in placebo and escitalopram treatment groups may be increased to ensure an adequate power.	Additional language to account for remote visits
13.1 Drug Accountability		In addition, sites will be provided a separate Investigational Product Curbside Pickup and Shipment Tracking Form to document pertinent study drug dispensing information each time a new shipment of study drug is shipped directly to a subject's residence, dispensed curbside at the site, or delivered to a subject's residence via site personnel. Sites will be instructed to submit this form to Syneos Health any time study drug is dispensed using these methods.	Additional language for remote visits.
17.1 Clinical Global Impression of Severity	1. Normal—not at all ill, symptoms of disorder not present past 7 days 2. Borderline mentally ill—subtle or suspected pathology 3. Mildly ill—clearly established symptoms with minimal, if any, distress or difficulty in social and occupational function 4. Moderately ill—overt symptoms causing noticeable, but modest, functional		Deleted for consistency as no other assessments are included in the protocol appendix.

CONFIDENTIAL

Location in Amended Protocol	Original Text (Final Protocol Version 2.0 dated 15 Mar 2019)	Revised Text in Amended Protocol (Protocol Version 3.0 dated 30 June 2020)	Rationale for Change
	
impairment or distress; symptom level may warrant medication
 
5. Markedly ill—intrusive symptoms that distinctly impair social/occupational function or cause intrusive levels of distress
 
6. Severely ill—disruptive pathology, behavior and function are frequently influenced by symptoms, may require assistance from others
 
7. Among the most extremely ill patients—pathology drastically interferes in many life functions; may be hospitalized
		
17.1 Prohibited Medication	
Hormones
 
Only thyroid hormone replacement, oral contraceptives, patch contraceptives, estrogen and progesterone replacement therapy are allowed.
	
Hormones
 
Reference to footnote b removed
 
Hormone therapy (including oral contraceptives for female subjects) should not be initiated or discontinued within the 3 months prior to screening.
	Update to align with changes in Section 8.4.8.1 for washout of antidepressant medication.
17.3 Telehealth		
17.3 Telehealth
 
For remote study visits subject data are collected via telephone or telehealth video calls using the technology provider.
 
Overall Design
 
In order to support the subject's education, engagement and activity completion in the study, subjects will participate by using their own mobile telephone. If the subject's own mobile telephone model and/or operating system does not meet the minimum technology requirements, if the subject does not have a device or chooses not to do video conferencing then regular
	Addition of information on data collection via telephone or video calls for remote visits.

CONFIDENTIAL

Allergan

SCT-MD-60

Version 3.0 Final

30 June 2020

Page 99 of 99

Location in Amended Protocol	Original Text (Final Protocol Version 2.0 dated 15 Mar 2019)	Revised Text in Amended Protocol (Protocol Version 3.0 dated 30 June 2020)	Rationale for Change
		
telephone contact will be allowed. Sites should remain consistent with either methods for each subject.
 
If the subject decides to use their own mobile device, the subject will be provided with a study-specific mobile application (app) to support reminders/notifications, activity completion, etc. This mobile app will be downloaded by the subject on their own mobile telephone from the Apple (iOS device) or Google Play Store (Android device) upon their receipt of a study-specific email with download hyperlink and unique study access code.
 
The study-specific mobile application (app) will support the subject to complete study-specific activities such as:
 
• Receive notifications for an ad-hoc telehealth call.• Conducting Telehealth Virtual Visits with the investigator and/or authorized site representative.	

CONFIDENTIAL

eCRF electronic case report form

ET end of treatment

GAD generalized anxiety disorder

LOCF last observation carried forward

MCH mean cell hemoglobin

MedDRA Medical Dictionary for Regulatory Activities

mITT modified Intent-to-Treat

MMRM mixed-effects model for repeated measures

MMRM-CAT categorical mixed effects model for repeated measures

NEAE newly emergent adverse event

OC observed cases

SAP SCT-MD-60

Allergan Page 7 of 53

PARS pediatric anxiety rating scale

PCS potentially clinically significant

PK pharmacokinetic

PT preferred term

QTc QT interval corrected for heart rate

QTcB QT interval corrected for heart rate using the Bazett formula

QTcF QT interval corrected for heart rate using the Fridericia formula

SAE serious adverse event

SAP statistical analysis plan

SE Standard Error

SI Le Système International d'Unités (International System of Units)

SID subject identification

SOC System Organ Class

TBL total bilirubin

TEAE treatment-emergent adverse event

ULN upper limit of normal laboratory reference range

Page 8 of 53

3.0 INTRODUCTION

This statistical analysis plan (SAP) provides a more technical and detailed elaboration of the statistical analyses of the efficacy and safety data as outlined and/or specified in the protocol of Study SCT-MD-60. Specifications of tables, figures, and data listings are contained in a separate document.

This is a randomized, multicenter, double-blind, flexibly-dosed, placebo-controlled parallel group study of escitalopram in the treatment of children (aged 7 through 11 years) and adolescents (aged 12 through 17 years) with generalized anxiety disorder (GAD).

The study design incorporates an up to 3 week screening period, an 8-week double-blind, acute treatment period, and a 1-week double-blind down taper period with a follow-up telephone contact 1 week after the end of the double-blind down taper period.

Approximately 430 subjects will be screened and a total of approximately 256 subjects are planned to be randomized in a 1:1 ratio to either escitalopram or placebo. The randomization schedule will be stratified by age at randomization (grouped as 7-11 years vs. 12–17 years) and sex, and blocked. The sample size may be increased based on the outcome of a blinded interim analysis but the number of subjects in each treatment arm will be capped at 160.

Subjects will begin with a 10 mg/day dose of escitalopram (taken orally) or matching placebo for the first 2 weeks of double-blind treatment. At the end of Week 2, subjects who can tolerate the current dose of 10 mg/day may have a dose escalation to 20 mg/day of escitalopram or matching placebo. Dose escalation will be at the investigator's discretion taking into account the Clinical Global Impression of Severity (CGI-S) score. Subjects who remain on the 10 mg/day dose of escitalopram or matching placebo will be evaluated again at Week 4 for a possible dose escalation to 20 mg/day at the investigator's discretion. Dose escalations cannot be made at any other time during the study. The dose may be decreased from 20 mg/day to 10 mg/day following discussion with the medical director if the subject does not tolerate the 20 mg/day dose. At the end of the treatment period or at early withdrawal, subjects will enter a 1-week double-blind down taper period.

For subjects receiving escitalopram 10 mg/day, the doses given during the double-blind down taper period will be as follows:

• Week 9: Subjects will receive placebo.

For subjects receiving escitalopram 20 mg/day, the doses given during the double-blind down taper period will be as follows:

Week 9: Subjects will receive 10 mg/day.

AbbVie Escitalopram

SAP SCT-MD-60 Allergan

Page 9 of 53

Subjects randomized to the placebo arm will receive matching placebo during the double-blind acute treatment period. Subjects evaluated at the end of Week 2 and Week 4 and tolerating 10 mg/day matching placebo may be indicated for dose escalation by the investigator but in a blinded fashion will continue to receive matching placebo. Subjects receiving placebo will follow a similar down tapering schedule at the end of the double-blind acute treatment period.

A follow-up telephone contact will take place 1 week after the end of the double-blind down taper period.

[figure not shown]
A blinded interim analysis will be conducted when 75% of randomized subjects have either completed or discontinued the study in order to check the assumptions in the sample size calculation. Based on this, the sample size may be increased to ensure an adequate power. However, due to the difficulties in recruiting pediatric subjects with GAD, the number of subjects in each treatment arm will be capped at 160.

The study design is shown in Figure 1.

Page 10 of 53

3.1 STUDY DESIGN

Figure 1. Flow Chart of the Study

Page 11 of 53

3.2 SCHEDULE OF ASSESSMENTS

Period	Screening Period		Double-blind Down Taper Period	Follow-up					
Visit	1	2	3	4	5	6	7/ET ^a	8 _p	Telephone Contact
Day/Week	Day -21 to -1	Baseline Day 1	Week 1°	Week 2°	Week 4 ^c	Week 6 ^c	Week 8/ET ^c	Week 9°	Week 10 ^c
Subject Informed Consent/Assent	X								
Parent Informed Consent	X								
Inclusion/Exclusion Criteria	X	X							
Demographics	X								
Medical History	X								
Psychiatric History	X								
Medication History	X								
MINI Kid	X								
Physical Examination	X						X		
Body Mass Index (BMI)	X				X		X		
Randomization		X							
Vital Signs ^d	X	X	X	X	X	X	X	X	
Electrocardiogram (ECG)	X						X		
Urine Drug Screen	X						X		
Screen for HBsAg, HCVAb, HIV	X								
Clinical Chemistry including Thyroid	Xe						X		
Hematology	X						X		
Urinalysis	X						X		
Pregnancy Test ^f	X	X					X		
C-SSRS	X	X	X	X	X	X	X	X	
CGAS	X	X	X	X	X	X	X		
PARS	X	X		X			X		
CGI-S	X	X		X			X		
Global COVID-19 Impact Assessment ⁸	X	X	X	X	X	X	X		

Page 12 of 53

Evaluate for Dose Escalation ^h				X	X				
PK Blood Samples ⁱ					X		X		
Dispense Study Drug		\mathbf{X}^{j}	X	X	X	X	X		
Study Drug Accountability			X	X	X	X	X	X	
Adverse Events		4							
Concomitant Medications	4								

Abbreviations: BMI = body mass index; CGAS = Children's Global Assessment Scale; CGI-S = Clinical Global Assessment of Severity; COVID-19 = coronavirus disease 2019; C-SSRS = Columbia-Suicide Severity Rating Scale; ECG = electrocardiogram; ET = End of Treatment; HBsAg = hepatitis B surface antigen; HCVAb = hepatitis C virus antibody; HIV = human immunodeficiency virus; MINI Kid = Mini-International Neuropsychiatric Interview for Children and Adolescents; PARS = Pediatric Anxiety Rating Scale; PK = pharmacokinetic.

^a End of Treatment or Early Withdrawal.

^b If a site becomes aware of any adverse events after study completion (occurring outside of a defined study visit, including any contact up to 30 days after study completion), all adverse events reported by the patient or patient representative or observed or otherwise identified by the investigator or other study personnel must be documented.

^c Visit window ± 3 days. Refer to Section 8.2.2.1, Table 1 of the protocol for visit windows for safety assessments (physical examination, BMI, vital signs, ECG, urine drug screen, clinical chemistry including thyroid, hematology, urinalysis, pregnancy test) and/or PK assessments missed due to remote visits.

^d Vital signs (blood pressure, pulse rate, temperature, and respiration rate) will be recorded at every visit. Height and weight will be recorded at Visit 1 (Screening), Visit 5 (Week 4), and Visit 7 (Week 8/ET) only.

^e Fasting blood sample.

^fA serum pregnancy test will be performed at Visit 1 (Screening); a urine pregnancy test will be performed at Visit 2 (Baseline) and Visit 7 (Week 8/ET) for females of childbearing potential.

g To be completed last after all other study assessments.

h Subjects who can tolerate the current dose of 10 mg/day may have a dose escalation to 20 mg/day at the investigator's discretion taking into account the CGI-S score. For PK blood sampling for assented/consented subjects at Visit 5 (Week 4) and Visit 7 (Week 8/ET), 2 blood samples per subject will be collected at each of these visits for escitalopram and S-demethylcitalopram analysis at the following times: Visit 5 (Week 4): for subjects receiving dose in the morning, at 0 h (predose) and ≥ 1 h postdose and for subjects receiving dose in the evening, 2 samples at random times during the visit (i.e., postdose from the dose received the previous evening), collected at least 2 hours apart from each other; and Visit 7 (Week 8/ET): 2 samples at random times during the visit (i.e., postdose from the dose received in the morning or the previous evening), collected at least 2 hours apart from each other.

^j Subjects should take their first dose of study drug in clinic.

Page 13 of 53

3.3 SCHEDULE OF ASSESSMENTS THAT CAN BE DONE REMOTELY

Period		Double-blind Acute Treatment Period						
Visit	2	3	4	5	6	7/ET ^a	8 _p	Telephone Contact
Day/Week	Baseline Day 1	Week 1 ^c	Week 2 ^c	Week 4 ^c	Week 6 ^c	Week 8/ET ^c	Week 9°	Week 10 ^c
Inclusion/Exclusion Criteria	X							
Randomization	X							
C-SSRS	X	X	X	X	X	X	X	
CGAS	X	X	X	X	X	X		
PARS	X		X			X		
CGI-S	X		X			X		
Global COVID-19 Impact Assessment ^a	X	X	X	X	X	X	X	
Evaluate for Dose Escalation ^e			X	X				
Dispense Study Drug ^f	Xg	X	X	X	X	X		
Study Drug Accountability		X	X	X	X	X	X	
Adverse Events	◄							
Concomitant Medications								

Abbreviations: CGAS = Children's Global Assessment Scale; CGI-S = Clinical Global Assessment of Severity; COVID-19 = coronavirus disease 2019; C-SSRS = Columbia-Suicide Severity Rating Scale; ET = End of Treatment; PARS = Pediatric Anxiety Rating Scale; PK = pharmacokinetic.

Notes for Remote Study Visits:

- The Baseline Visit can be remote but it is not preferred. For all female subjects of childbearing potential, the Baseline Visit must take place as an in-clinic visit with all assessments outlined in Section 8.1.2 of the protocol.
- Subject data are collected via telephone or telehealth video calls using a technology provider. Sites should remain consistent with either method (video or telephone) for each subject.
- In-clinic safety and PK assessments missed due to remote visits may be collected per Section 8.2.2.1, Table 1 of the protocol.
- ^a End of Treatment or Early Withdrawal.

- ^c Visit window ± 3 days.
- ^d To be completed last after all other study assessments.
- ^e Subjects who can tolerate the current dose of 10 mg/day may have a dose escalation to 20 mg/day at the investigator's discretion taking into account the CGI-S score.
- ^f For remote visits study drug will be sent to subjects via curbside (preferred) or courier.

^b If a site becomes aware of any adverse events after study completion (occurring outside of a defined study visit, including any contact up to 30 days after study completion), all adverse events reported by the patient or patient representative or observed or otherwise identified by the investigator or other study personnel must be documented.

Allergan

SAP SCT-MD-60

Page 14 of 53

g In case of a remote Baseline Visit, subjects will receive and take their first dose of study drug via curbside (preferred) or they will receive it by courier and take it at home.

Page 15 of 53

4.0 STUDY OBJECTIVES

4.1 PRIMARY OBJECTIVE

The primary objective of this study is to assess the safety and efficacy of escitalopram relative to placebo in the acute treatment of children (aged 7 through 11 years) and adolescents (aged 12 through 17 years) who meet criteria for GAD as defined in the Diagnostic and Statistical Manual of Mental Disorders, Fifth Edition (DSM-5).

4.2 SECONDARY OBJECTIVE

The secondary objective of this study is to characterize the pharmacokinetic (PK) profile of escitalopram in the pediatric population (aged 7 through 17 years).

4.3 EXPLORATORY OBJECTIVE

The exploratory objective of this study is to assess the exposure/dose-response relationship.

Page 16 of 53

5.0 SUBJECT POPULATIONS

Five populations will be considered in the statistical analysis of the study.

5.1 SCREENED POPULATION

The Screened Population will consist of all subjects who underwent a Screening Visit and received a subject number, and signed the informed consent form.

5.2 RANDOMIZED POPULATION

The Randomized Population will consist of all subjects in the Screened Population who were randomized to a treatment group in the study. Randomized treatment will be utilized for the summaries of Randomized Population by treatment.

5.3 SAFETY POPULATION

The Safety Population will consist of all subjects in the Randomized Population who took at least one dose of study medication. Actual treatment received based on the treatment received the most during the double-blind acute treatment period (>50% of doses) will be utilized for the summaries of Safety Population by treatment. If placebo and escitalopram are received an equal number of times, escitalopram will be considered the actual treatment received.

5.4 MODIFIED INTENT-TO-TREAT (MITT) POPULATION

The mITT Population is defined as all subjects who were randomized and received at least one dose of study medication, and have both baseline and at least one post-baseline primary efficacy measure [ie, Pediatric Anxiety Rating Scale (PARS) severity score]. The mITT population will be used for all of the efficacy analyses. Randomized treatment will be utilized for the summaries of mITT Population by treatment.

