8.3 Selection of Study Population

8.3.1 Number of Planned Subjects

A total of approximately 430 subjects will be screened and approximately 256 subjects (128 per treatment arm) are planned to be randomized in approximately 40 centers in the United States. It is assumed that approximately 115 subjects per treatment arm will be evaluable (ie, have at least one postbaseline assessment).

A blinded interim analysis will be conducted when 75% of randomized subjects have either completed or discontinued the study in order to check the assumptions in the sample size calculation. Based on this, the sample size may be increased to ensure an adequate power due to variance assumption deviation as well as increased variance due to COVID-19 remote visits. However, due to the difficulties in recruiting pediatric

CONFIDENTIAL

subjects with GAD, the number of subjects in each treatment arm will be capped at 160 (see [Section 11.8](#)).

Re-screening of subjects who do not meet the entry criteria is not allowed, except for the reasons outlined in [Section 8.3.4](#). A subject can only be re-screened once.

The statistical considerations on which the sample size is based are provided in [Section 11.9](#).

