11.9 Determination of Sample Size

The sample size estimate was constructed using a simulation approach as described in Lu K. (2012)¹⁸.

The primary efficacy parameter will be the change from baseline to Week 8 of the double-blind treatment period in PARS total score. To detect an effect size (treatment group difference of 2.30 units relative to pooled standard deviation of 5.79¹⁹) of 0.39, a sample size of 128 subjects in the escitalopram treatment group and 128 subjects in the placebo group will provide 85% power based on an MMRM model using simulation

CONFIDENTIAL

method. The simulation assumed a correlation of 0.7 between the repeated measures, and a common dropout rate of 14%, based on historical data of escitalopram in pediatric subjects.

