For the LOCF approach, only the postbaseline PARS severity score for GAD will be imputed; individual item scores will not be carried forward to derive the PARS severity score. Baseline total score will be carried forward only for the missing scores immediately after baseline. If all the postbaseline values are missing, the baseline value will not be carried forward. The LOCF approach is based on an analysis-of-covariance (ANCOVA) model including treatment group and pooled study center as factors and baseline PARS severity score as a covariate

Another sensitivity analysis using a pattern-mixture model approach based on non-future dependent missing value restrictions (Kenward et al., 2003) will be performed to assess the robustness of the primary MMRM results to the possible violation of the missing-at-random assumption. The details of this sensitivity analysis are as follows:

The pattern for the pattern-mixture model will be defined by the subject's last visit with an observed value. The observed PARS severity score at a visit is assumed to have a linear relationship with the subject's prior measurements. The missing values will be imputed under the assumption that the distribution of the missing observations differs from that of the observed only by a shift parameter value Δ . The dataset with missing values imputed will be analyzed using an analysis of covariance (ANCOVA) model with treatment group and pooled study center as factors and baseline PARS severity score as a covariate for between–treatment group comparisons at Week 8. The imputation of missing values and the analysis will be performed multiple times and the inference of this sensitivity analysis will be based on the combined estimates using the standard multiple imputation technique. The shift parameter values Δ for the multiple imputation will start at 0 and increase by 1 to 6 or until a tipping point is reached (ie, the p-value switches from ≤ 0.05 to ≥ 0.05), whichever is higher.

Page 26 of 53

More details of the proposed pattern-mixture model approach (e.g., the models for the pattern-specific identifiable densities and the unidentified conditional distributions, the shift parameter Δ , and the multiple imputation algorithm) are provided in Appendix I to this SAP.

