13.0 BLINDED INTERIM ANALYSIS

A blinded interim analysis will be conducted when approximately 75% of randomized subjects have either completed the study or discontinued from the study. The blinded interim analysis is to obtain an estimate of the pooled standard deviation of the change from baseline in the PARS score to Week 8 of the double-blind acute treatment period. The sample size will be re-estimated using simulation in the same manner as the original sample size as described in Section 14 using the estimated pooled standard deviation and dropout rate from the blinded interim analysis. If the estimated pooled standard deviation is larger than the assumed pooled standard deviation due to assumption deviation as well as COVID-19 remote visits or dropout rate is increased, the sample size in placebo and escitalopram treatment groups may be increased to ensure an adequate power. However, due to the difficulties in recruiting pediatric subjects with GAD, the number of subjects in each treatment arm will be capped at 160.

As the sample size re-estimation requires only the pooled standard deviation and dropout rate to be updated, all data and personnel will remain blinded for the interim analysis. Randomization code will not be released for the sample size re-estimation. There are no potential unblinding issues in the sample size re-estimation. As this is a blinded re-estimation, there is no impact on the overall Type I error rate of the study.

SAP SCT-MD-60 Allergan

Page 40 of 53

14.0 DETERMINATION OF SAMPLE SIZE

The sample size estimate was constructed using a simulation approach as described in Lu K. (2012).

The primary efficacy parameter is the change from baseline to Week 8 of the double-blind acute treatment period in PARS total score. To detect an effect size (treatment group difference of 2.30 units relative to pooled standard deviation of 5.79) of 0.39, a sample size of 128 subjects in the escitalopram treatment group and 128 subjects in the placebo group will provide 85% power based on an MMRM model using simulation method. The simulation assumed a correlation of 0.7 between the repeated measures, and a common dropout rate of 14%, based on historical data of escitalopram in pediatric subjects.

SAP SCT-MD-60 Allergan

Page 41 of 53

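### Dosed subjects with a baseline PARS but no later PARS fall outside mITT, and so outside both checks on the missing-at-random assumption

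*SAP*

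**What the plan says.** SAP 5.4 admits to mITT only subjects who were randomized and dosed and who "have both baseline and at least one post-baseline primary efficacy measure". It then states: "The mITT population will be used for all of the efficacy analyses". Protocol 11.1.1.4 has the same definition and the same rule.

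The schedules (Protocol 8.1.2, SAP 3.2) place PARS after baseline only at Week 2 and at Week 8/ET. Of the efficacy scales, Protocol 9.2.1 lists only the CGAS at Week 1. Protocol 8.3.5 asks subjects who withdraw to complete the End of Treatment visit, which includes PARS.

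SAP 9.1.2 names two analyses to probe missing at random: LOCF with ANCOVA, and a pattern-mixture model with a shift Δ. Neither is given a population other than mITT. For LOCF the SAP says: "If all the postbaseline values are missing, the baseline value will not be carried forward".

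On numbers, Protocol 8.3.1 says "approximately 256 subjects (128 per treatment arm) are planned to be randomized" and that "approximately 115 subjects per treatment arm will be evaluable (ie, have at least one postbaseline assessment". Protocol 11.9 and SAP 14 assume "a common dropout rate of 14%, based on historical data of escitalopram in pediatric subjects".

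**The concern.** SAP 9.1.1 describes the target population as children and adolescents with GAD who meet the entry criteria. It treats data after discontinuation, for any reason, as missing at random. (Protocol 11.5.1.1.1 instead names mITT as the target population.) On the SAP's description the assumption extends to subjects who stop before any post-baseline PARS, yet it is never tested on them.

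Membership of mITT is decided after randomization. If early stopping differs between arms, the Week 8 comparison rests on a set selected after randomization. Neither sensitivity analysis can register that imbalance, because the subjects concerned are absent from both. A report that the result is robust to missing data would then cover only the dropouts who had already supplied a post-baseline score.

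The method itself does not require the exclusion. Appendix I builds on the marginal distribution of the baseline measurement, defines the first missing value for s = 2,...,T and imputes for patterns t = 1,...,T-1. With y1 taken as baseline, pattern 1 is the baseline-only pattern, and the mITT rule empties it.

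**Working it through.** **Inputs.** 128 randomized and about 115 evaluable per arm (Protocol 8.3.1); dropout 14%, difference 2.30, SD 5.79, power 85% (Protocol 11.9, SAP 14); two-sided α 0.05 (SAP 9.1.2). SAP 14 also says "The simulation assumed a correlation of 0.7 between the repeated measures".

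**Reproducing the 85%.** With two post-baseline PARS visits and monotone dropout, 1/n_eff = (1 - r²)/n_wk8 + r²/n_wk2 with r = 0.7, and power = Φ((2.30/5.79) × √(n_eff/2) - 1.96).

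- A: 14% of 128 drop out and 115 have Week 2. 0.51/110 + 0.49/115 gives n_eff 112.4, power 84.6% (simulation 84.1%).
- B: 14% of 128 drop out and all 128 have Week 2. n_eff 118.1, power 86.3% (simulation 86.0%).
- C: 14% of the 115 drop out on top of the 13, so 99 reach Week 8. n_eff 106.2, power 82.5% (simulation 82.2%).

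A and B both reproduce the stated power. C misses it by about 2.5 points in a two-visit approximation. This favours taking 14% of the 128, but it cannot separate A from B. The 13 subjects without a post-baseline assessment therefore rest on Protocol 8.3.1 alone.

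**Coverage per arm.** Non-evaluable: 128 - 115 = 13. Dropouts at 14% of 128: 17.9.

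| Reading | Dropouts outside both checks | All dropouts | Covered |
|---|---|---|---|
| 14% of 128; all 13 are dosed dropouts | 13 | 17.9 | 4.9, about 5 of 18 |
| As above, but a third of the 13 never dosed and not counted as dropouts | 13 × 2/3 = 8.7 | 17.9 | 9.2, about 9 of 18 |
| 14% of 115, on top of the 13 | 13 | 13 + 16.1 = 29.1 | 16.1, about 16 of 29 |

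If the approximate 115 is really 113 to 117, the first row becomes 2.9 to 6.9 of 17.9. Protocol 8.3.1 also counts any post-baseline assessment. A subject with only a Week 1 CGAS is evaluable there but not in mITT, which would lower coverage.

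**Effect of a shift of 6 on one arm mean (first reading).** Six is the least upper end of the SAP grid.

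- Under the plan: 5 dropouts have Week 8 as their first missing value and take the full shift, so 6 × 5/115 = 0.26 points.
- With the baseline-only pattern: Appendix I adds Δ in full to the first missing value, here Week 2. It reaches Week 8 through the regression on Week 2, and Δ is added again only with probability δ. The slope is not given. I assume 0.41 (0.7/1.7, from a correlation of 0.7 among baseline, Week 2 and Week 8) to 0.70, with δ about 5/115 = 0.043.
- Week 8 shift per baseline-only subject: 6 × (0.41 + 0.043) = 2.7 to 6 × (0.70 + 0.043) = 4.5.
- Arm mean: (5 × 6 + 13 × 2.7)/128 = 0.51 to (5 × 6 + 13 × 4.5)/128 = 0.69 points.

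Against the design difference of 2.30, these are 11% under the plan and 22% to 30% with the wider set. Under the second reading the plan already moves 6 × 9/115 = 0.47, so the gain is smaller.

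**Effect on the treatment difference.** Appendix I uses one common Δ with no arm-specific values, so equal dropout largely cancels. Each extra baseline-only subject in one arm adds about 2.7/128 = 0.02 to 4.5/128 = 0.04 points at a shift of 6. Under mITT that contribution is zero whatever the imbalance.

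**The case against.** **Coverage.** A reader might infer that the plan itself shows only 5 of 18 dropouts covered. It does not. That figure joins an evaluability allowance and a simulation dropout rate that the documents never link, and the stated power is also reproduced if every dropout has a Week 2 score. This objection stands, so the count can only be conditional.

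**Size.** It is tempting to give all 18 dropouts the full shift: 18/128 × 6 = 0.84 points, or 37% of 2.30. Appendix I, Step 2, does not support this, because a Week 2 shift reaches Week 8 only through the regression and a small mixture term. Nor must the test end at 6: SAP 9.1.2 continues to the tipping point if that is higher.

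**Cause and bias.** A reader might infer that early stoppers leave because of the drug, or that the primary result is biased. The documents give no timing of or reasons for dropout and plan with a common rate. Baseline-only subjects supply no post-baseline outcome to the MMRM, and the estimand already assumes adherence with data missing at random.

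**Already handled.** The early-withdrawal visit includes PARS and may be remote, so stopping before Week 2 does not by itself remove a subject. SAP 6 reports mITT counts by arm and discontinuation reasons for the Safety Population. Both points stand in part. Subjects who do not return are still excluded. The tables do not isolate why dosed subjects fell out of mITT, and they cannot test the Week 8 result.

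**Conclusion.** The gap in scope is real and follows from the text alone: no provision lets either missing-at-random check include dosed subjects without a post-baseline PARS. Its extent is uncertain. Coverage is about 5 of 18 dropouts per arm if 14% applies to all 128 and the 13 are all dosed dropouts, about 9 of 18 if a third of the 13 were never dosed, and about 16 of 29 if the 14% comes on top of the 13.

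On the first reading and the assumed slopes, including these subjects would roughly double or more the movement of an arm mean at a shift of 6 (0.5 to 0.7 against 0.26 points). The treatment difference would move much less unless early stopping is unequal between arms. That imbalance is what the present analysis cannot register. The point concerns the reach of the sensitivity analysis and gives no reason to change the primary analysis.

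**What to change.** Keep the primary MMRM on mITT. Run the pattern-mixture analysis, or a second version of it alongside the mITT one, on all randomized subjects with at least one dose and a baseline PARS, analysed as randomized. Define a baseline-only pattern and impute its Week 2 and Week 8 values by Appendix I, Steps 1 and 2.

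Amend SAP 5.4 and 9.1.2 accordingly. Record the change in SAP 17, since Protocol 11.1.1.4 also reserves all efficacy analyses to mITT and SAP 17 at present lists only the z-score change. In the disposition tables already planned in SAP 6, add the stopping reasons, by arm, of dosed subjects excluded from mITT.

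This is a cheap improvement: SAP wording and a little programming, with no new data. The downside is that the tipping point may come at a smaller shift, so the robustness statement may look less favourable.
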